Study size:	There are 25,291 patients with a prescription claim for tiotropium (1.25mcg, October 2015-May 2020) identified for analysis and 1,125,657 patients with ICS/LABA prescription claims (July 2014-May 2020). After excluding patients with COPD there are 17,882 patients in the Tio group and 921,804 patients in the ICS/LABA group. Further inclusion-exclusion criteria as well as restricting the Tio group to those with concurrent ICS monotherapy, will be applied to arrive at the final sample.		

Proprietary confidential information © 2021 Boehringer Ingelheim International GmbH or one or more of its affiliated companies

Name of company: Boehringer Ingelheim			
Name of finished medicinal product: Spiriva Respimat			
Name of active ingredient: Tiotropium			
Protocol date: 12 May 2021	Study number: 0205-0547	Version/Revision: 1.0	Version/Revision date: 12 May 2021

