9. RESEARCH METHODS

9.1 STUDY DESIGN

1. Patients with least two asthma diagnosis (ICD 9 CM: 493.xx or ICD 10: J45-J45.999) will be included.
2. Patients will be required to be concurrently on ICS+Tiotropium (specifically Tiotropium Respimat® 1.25 mcg) or ICS/LABA.
3. Patients with least two diagnosis of COPD at any time during the study period will be excluded.
4. Patients less than 12 years of age will be excluded.
5. Patients will be required to have enrollment for at least 6 months prior to ICS+Tio or ICS/LABA use.
6. Patients on biologics within 6 months prior to ICS+Tio or ICS/LABA use will be excluded.
7. Patients with prior Tio or ICS/LABA use during the 6-month baseline period will be excluded.
8. Patients with urinary bladder obstruction, urinary retention, and glaucoma will be excluded.
9. After the PSM process, unmatched patients will be excluded.

Patients will be classified into two groups based on the exposure on the index date: 1. ICS+Tio; and 2: ICS/LABA. The date of concurrent medication initiation will be defined as the index date based on the date of the first prescription claim defining their add-on medication. We will record various baseline measures, including demographics such as gender, age, and region, comorbidity level defined using Charlson Comorbidity Index (CCI), other specific comorbidities not included in the CCI ([Table 1](#)), inhaled medication use, and control level as defined in Table 1. Additionally, we will classify patients based on their daily ICS dose levels as 'low dose ICS', 'medium dose ICS', and 'high dose ICS'. The dose levels will be assigned per GINA 2020 criteria (Global Initiative for Asthma. Global Strategy for Asthma Management and Prevention 2020). Medications that are available with only two dose level indications will be tagged as 'low' for the lower of the two dose levels, and 'high' for the highest dose level.

Proprietary confidential information © 2021 Boehringer Ingelheim International GmbH or one or more of its affiliated companies

Table 1: Baseline Parameters and Variable Definitions

Variable Name and Type	Description and Definition	Covariate Adjustment Method
Demographics	Age (5-year increments), Gender,	PSM
Region	Region (Northeast, Midwest, South, West)	PSM
CCI	Charlson Comorbidity Index score	PSM
Inhaled medication use	Identified using unique claims during the baseline period	PSM

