9.3.2.2 Secondary endpoints

Secondary endpoints will include:

- Time to first moderate-or-severe exacerbation
 - Any systemic corticosteroid use or
 - A hospitalization with a primary diagnosis of asthma or
 - An ER visit with a primary diagnosis of asthma
- Proportion of patients with exacerbation
- Rate of exacerbation at 6 months and one year
- Proportions of patients with Health care resource utilization (HCRU). HCRU is defined as hospitalizations, emergency room (ER) visits, and outpatient visits during follow-up, all-cause and asthma related.
- Mean monthly HCRU (including frequency of hospitalizations, ER visits, OP visits)
- Proportion of patients with use of rescue medications (defined as patients with one or more SABA claims during the follow-up period)

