9.3.3 Covariates

The covariates included in the PSM will be

- Gender
- Age group
- Region
- ICS dose level
- Control level
- Rescue medication use
- Comorbidities included in the Charlson Comorbidity Index
- ICS history (yes/no)
- ICS history duration
- Season of index date
- Index year
- Baseline all-cause resource use (presence vs. absences of hospitalizations, or ER visits, or outpatient visits)
- Baseline other asthma medications (use vs. no use)

Proprietary confidential information © 2021 Boehringer Ingelheim International GmbH or one or more of its affiliated companies

- Baseline overall medication history (polypharmacy defined as number of unique medications)
- Insurance type
- Hypertension
- Gastroesophageal reflux disease
- Allergic Rhinitis
- Obesity
- Sinusitis
- Obstructive sleep apnea
- Cardiovascular disease
- Diabetes
- Renal failure
- Arthritis
- Osteoporosis
- Depression
- Cancer (excluding basal cell carcinoma)
- Baseline pneumonia diagnosis
- Baseline acute bronchitis diagnosis
- Diagnosis of dyspnea during baseline identified using ICD 9 786.0x and ICD 10 R06.0x
- Diagnosis of alcohol dependence during baseline identified using ICD 9 303.xx, 305.0x and ICD 10 F10.xx
- Smoking dependence during baseline identified using ICD 9 305.1 and ICD 10 F17.xx

In addition to the key independent variable of interest (ICS+TIO vs ICS/LABA group), we will include time varying medication exposure as a covariate in the regression.

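### COPD is the only chronic lung disease excluded and no other is a named matching covariate, which leaves a small, unchecked confounding risk in the steroid-driven secondary endpoint and in all-cause resource use

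*Combined protocol and SAP*

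**What the plan says.** **Eligibility (section 9.1).** Entry rests on asthma codes: "Patients with least two asthma diagnosis (ICD 9 CM: 493.xx or ICD 10: J45-J45.999) will be included". Two criteria exclude on other diagnoses: "Patients with least two diagnosis of COPD at any time during the study period will be excluded" and "Patients with urinary bladder obstruction, urinary retention, and glaucoma will be excluded". Nothing bars a second chronic lung disease other than COPD.

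**Matching covariates (Table 1 and section 9.3.3).** The respiratory conditions named are pneumonia, acute bronchitis and dyspnea, which are acute conditions or a symptom, plus obstructive sleep apnea. Arthritis, osteoporosis and many others are named; bronchiectasis, cystic fibrosis, interstitial lung disease and sarcoidosis are not. The Charlson index enters too, in two forms: section 9.3.3 has "Comorbidities included in the Charlson Comorbidity Index", while Table 1 has "Charlson Comorbidity Index score". Neither place lists the items.

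**Endpoints.** The primary endpoint (section 9.3.2.1) counts a hospitalization or ER visit only with asthma as primary diagnosis. The secondary moderate-or-severe endpoint (section 9.3.2.2) adds "Any systemic corticosteroid use or", with no diagnosis attached. HCRU is analysed both for all causes and for asthma. In Table 1, a single oral corticosteroid prescription is enough to class baseline asthma as not well controlled.

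**The concern.** A patient who has two asthma codes and also a chronic lung disease other than COPD is eligible. A steroid course given for that other disease is then a moderate exacerbation in the secondary analysis. At baseline it also makes the patient look like one with uncontrolled asthma, so the two can be matched to each other. Admissions and visits for the other disease enter all-cause HCRU.

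This matters for the comparison only if such patients are more frequent in one arm after matching. If they were more frequent under ICS+Tio, the secondary hazard ratio and all-cause HCRU would be biased against ICS+Tio. The plan would not detect it, because standardized mean differences (SMDs) are planned only for recorded baseline covariates, and these diseases are not recorded by name. Section 9.9 mentions misclassification and limited clinical history in general terms, but not this.

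**Working it through.** **Step 1. What the plan's own counts show about COPD.** Section 9.5 starts from 25,291 tiotropium and 1,125,657 ICS/LABA patients. It then gives: "After excluding patients with COPD there are 17,882 patients in the Tio group and 921,804 patients in the ICS/LABA group".

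- Tiotropium: 25,291 − 17,882 = 7,409 removed; 7,409 / 25,291 = 29.3%.
- ICS/LABA: 1,125,657 − 921,804 = 203,853 removed; 203,853 / 1,125,657 = 18.1%.
- Ratio 0.2930 / 0.1811 = 1.62. Difference 11.2 points (95% CI 10.6 to 11.8).
- SMD = (p1 − p0) / √{[p1(1 − p1) + p0(1 − p0)] / 2} = 0.27, against the plan's limit of 0.1.

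So the one chronic lung disease that the plan counts was clearly unequal in the raw pools. The documents give no count for any other.

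**Step 2. Which endpoints are open.**

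| Event caused by another lung disease | Primary | Moderate-or-severe | All-cause HCRU |
|---|---|---|---|
| Steroid course | no | yes | only through any visit |
| Admission or ER visit coded to that disease | no | no | yes |

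Admissions would reach the exacerbation endpoints only if miscoded with asthma as primary diagnosis. Asthma-related HCRU is not defined further; I take it to require an asthma diagnosis.

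**Step 3. Size under stated assumptions.** For an unmatched yes/no confounder with prevalence p1 (ICS+Tio) and p0 (ICS/LABA), and rate ratio RR for a steroid course, the approximate bias factor is

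[1 + p1(RR − 1)] / [1 + p0(RR − 1)].

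The prevalence p0 and RR are my assumptions. The ratio p1/p0 = 1.62 is borrowed from COPD. For p0 = 2%, p1 = 3.24%:

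- RR = 2: 1.0324 / 1.02 = 1.012.
- RR = 3: 1.0647 / 1.04 = 1.024 (p1 unrounded).

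Range over other prevalences at the same ratio:

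| p0 | p1 | RR 2 | RR 3 |
|---|---|---|---|
| 1% | 1.6% | 1.006 | 1.012 |
| 2% | 3.2% | 1.012 | 1.024 |
| 3% | 4.9% | 1.018 | 1.035 |
| 5% | 8.1% | 1.029 | 1.056 |

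With p1 = p0 the factor is 1.000 throughout. At 3.24% against 2% the SMD is 0.077. That is below 0.1, so a balance table alone would pass it. This is why the flag belongs in the propensity model and not only in the table.

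**The case against.** The case against has four parts.

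1. **Charlson may already cover it.** Section 9.1 presents the named comorbidities as additional to the Charlson ones, so absence from the named list does not show absence from the propensity model. This stands. A reader might infer that no other lung disease is matched on; the documents support only that none is named. Equally, they do not show that one is covered, and matching on a summary score would not balance a particular disease.

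2. **The COPD contrast does not transfer.** The 29.3% and 18.1% come from raw prescription pools with different windows (October 2015 to May 2020 against July 2014 to May 2020). They precede the restriction to concurrent ICS monotherapy, the remaining criteria and matching. This also stands. A reader might infer that other lung diseases are unevenly split in the matched cohort; the counts make that plausible and no more.

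3. **Proxies help.** Matching on control status, all-cause use, pneumonia, acute bronchitis, dyspnea, smoking dependence and polypharmacy should give partial balance. This stands as a reason to expect a small effect. It is not a check.

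4. **The root is elsewhere.** Steroid use is not linked to asthma for any indication, and a few lung codes leave that unchanged. True, but it does not make these particular patients harmless.

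A larger bias is also tempting to quote: 6% against 2% with RR 3 gives 1.12 / 1.04 = 1.077, about 8%. It needs a threefold imbalance surviving the match (SMD 0.205). Nothing in the documents supports that, and it exceeds even the unmatched COPD ratio.

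**Conclusion.** The gap is real and minor. COPD is the only chronic lung disease excluded, no other is a named covariate, and balance on the others would go unexamined. The exposed results are the moderate-or-severe endpoint, through unlinked steroid courses, and all-cause HCRU, through visits and admissions. It would be wrong to read this as a threat to the primary endpoint, which correctly coded events of another lung disease cannot enter.

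The size is about 1-2% on the secondary ratio, and zero if prevalence is equal. It rests on three assumptions: 2% ICS/LABA prevalence, a two- to threefold steroid rate, and a COPD-like ratio of 1.62 persisting after matching. The documents confirm none of these for other lung diseases. Direction, against ICS+Tio, follows only if those diseases split as COPD did.

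**What to change.** - Add yes/no baseline covariates for bronchiectasis, cystic fibrosis, interstitial lung disease or sarcoidosis, and other chronic lung disease that is neither asthma nor COPD, pooled where rare. Enter them in Table 1, section 9.3.3, the propensity model and the SMD table.
- Add one sensitivity analysis of the moderate-or-severe and HCRU endpoints that excludes patients with any of these codes in the baseline period. Baseline codes keep the exclusion free of follow-up information.
- As a clarification, list the Charlson items and say whether they enter singly or as a score. That would settle what is already covered.

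The cost is a short code list and one re-run on claims already extracted, with slightly fewer patients in the sensitivity analysis. The primary analysis changes only by the added propensity terms.

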7. RATIONALE AND BACKGROUND

Asthma is associated with a significant burden on the healthcare system. More than half the population of asthma patients remains uncontrolled despite therapy, and uncontrolled asthma is associated with greater economic and health care burden (Braido et al. 2013; Peters et al. 2007). Stepwise treatment approach depending on control and severity levels has been the corner stone of asthma therapy. Regardless of severity level, patients with uncontrolled asthma are prone to exacerbations, increased use of systemic corticosteroids, rescue medications, deteriorating lung function (Chung et al. 2014), reduced quality of life, and increased health care resource use. In such cases, guidelines recommend increasing the dose of ICS product or use of ICS in combination with long-acting β 2-agonists (LABA), and/or other add-on therapy such as with a long-acting muscarinic antagonist (LAMA), leukotriene receptor antagonists (LTRA), biologics or oral corticosteroids. Treatment strategies that rely on step treatment may not always be sufficient in controlling asthma.

Given the unmet needs, other therapeutic options should be considered in this population. In investigating Tiotropium (Handihaler and Respimat) for the treatment of asthma, 6 clinical trials (found similar responses in lung function and exacerbations when comparing ICS/Tiotropium to ICS/LABA. In a randomized controlled trial of moderate asthma patients, Kerstjens et al 2015 reported a lower rate of exacerbations among patients with ICS/Tiotropium when compared to ICS/Salmeterol (ICS/LABA) however formal comparisons could not be made since the ICS/salmeterol group was included to provide a standard add-on active comparator and was not part of the inferential analysis. Kerstjens et al study concluded that “Once-daily tiotropium as add-on treatment to medium-dose inhaled corticosteroids provided significant improvements in lung function and asthma control that were similar to those recorded for twice-daily salmeterol. In summary, RCTs have found

Proprietary confidential information © 2021 Boehringer Ingelheim International GmbH or one or more of its affiliated companies
similar responses in terms of lung function and exacerbations between patients on
ICS/Tiotropium and ICS/LABA.

NHLBI recommendations: Stepwise approach for management of asthma in patients ≥ 12 years

Treatment	Intermittent Asthma		Management of Persistent Asthma in Individuals Ages 12+ Years				

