Control Status: Not Well Controlled or Well Control	
“Not Well Controlled” if patient has any one of the following events
 
 • Prescription for OCS • Asthma-related ER • Asthma-related hospitalizations 
“Well controlled” if patient has none of the above events
 
(Ref: Stempel JACI 2005)
	PSM
ICS history	Defined by use of ICS monotherapy prior to index date	PSM
ICS history duration	Days on ICS monotherapy prior to index date	PSM
ICS dose level	Daily dose of ICS classified as low dose ICS, medium dose ICS, and high dose ICS	PSM
Season	Season of cohort entry (Summer, Spring, Fall, Winter)	PSM
Index year	Year of the index date	PSM
All-cause resource use	All-cause hospitalizations, ER visits, outpatient visits	PSM
Other asthma medications	Leukotriene modifiers	PSM
Medication history	Polypharmacy calculated based on number of unique medications	PSM
Insurance type	Identified using payer type data field	PSM
Hypertension	Identified using appropriate ICD codes. Coded as binary (yes/no) variables	PSM
Allergic rhinitis	Identified using appropriate ICD codes. Coded as binary (yes/no) variables	PSM
Sinusitis	Identified using appropriate ICD codes. Coded as binary (yes/no) variables	PSM
Obstructive sleep apnea	Identified using appropriate ICD codes. Coded as binary (yes/no) variables	PSM
Gastro-esophageal reflux disease	Identified using appropriate ICD codes. Coded as binary (yes/no) variables	PSM
Obesity	Identified using appropriate ICD codes. Coded as binary (yes/no) variables	PSM
Cardiovascular disease	Identified using appropriate ICD codes. Coded as binary (yes/no) variables	PSM
Diabetes	Identified using appropriate ICD codes. Coded as binary (yes/no) variables	PSM

Proprietary confidential information © 2021 Boehringer Ingelheim International GmbH or one or more of its affiliated companies

Table 1: Baseline Parameters and Variable Definitions (cont)

Variable Name and Type	Description and Definition	Covariate Adjustment Method
Renal failure	Identified using appropriate ICD codes. Coded as binary (yes/no) variables	PSM
Arthritis	Identified using appropriate ICD codes. Coded as binary (yes/no) variables	PSM
Depression	Identified using appropriate ICD codes. Coded as binary (yes/no) variables	PSM
Osteoporosis	Identified using appropriate ICD codes. Coded as binary (yes/no) variables	PSM
Cancer (excluding basal cell carcinoma)	Identified using appropriate ICD codes. Coded as binary (yes/no) variables	PSM

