Pneumonia	Identified using appropriate ICD codes. Coded as binary (yes/no) variables	PSM
Acute bronchitis	Identified using appropriate ICD codes. Coded as binary (yes/no) variables	PSM
Dyspnea	Identified using appropriate ICD codes. Coded as binary (yes/no) variables	PSM
Alcohol dependence	Identified using appropriate ICD codes. Coded as binary (yes/no) variables	PSM
Smoking dependence	Identified using appropriate ICD codes. Coded as binary (yes/no) variables	PSM

Using propensity score matching (PSM) technique, we will develop matched cohorts of patients between the ICS+Tio and ICS/LABA groups. We will conduct 1:2 matching using nearest neighbor matching approach. Upon completion of matching, we will assess whether the cohorts are balanced by examining the statistically significant differences at $p < 0.05$. We will also assess balance by calculating standardized mean differences (SMD). An SMD < 0.1 will be considered balanced. Follow-up time will be calculated between index date and 'Censor date' which will be defined as the date of either one of the following events: 1. Date of first exacerbation, 2. Date of medication switch, 3. Discontinuation of medication (defined as date of prescription claim plus days' supply, plus 50% additional days), 4. Enrollment end date, or 5. Last date available in the dataset/End of study period. In this "new user", study design, primary analysis will be an "as-treated" analysis. In order to attribute events and outcomes to patients during the time that they are exposed to treatment (based on days-supply of prescription claims + a buffer window) as well as account for differences in inter-group adherence levels, we will use a time-varying covariate approach to classify drug exposure time for each comparator drug during follow up. This approach has been chosen to minimize bias based on potentially large differences in medication adherence rates, by only attributing outcomes to the time in which patients have medication in their possession based on days' supply as described below. For each individual study drug, we will identify and define medication exposure and non-exposure windows during the follow-up time for each medication using the date of prescription filled plus the days' supply listed on the prescription claim plus 50% additional days (to account for residual doses in canister, poor real-world adherence and latency of drug effects). For example, exposure start and stop dates

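### The new-user washout names only Tio and ICS/LABA, so baseline users of another LAMA can enter either arm as new users, and the rule is ambiguous for other tiotropium products and separate LABA inhalers

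*Combined protocol and SAP*

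**What the plan says.** Section 9.1 describes the design as follows: "In this 'new user', study design, primary analysis will be an 'as-treated' analysis". Two eligibility criteria in that section concern earlier drug use.

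- Criterion 7: "Patients with prior Tio or ICS/LABA use during the 6-month baseline period will be excluded".
- Criterion 6: "Patients on biologics within 6 months prior to ICS+Tio or ICS/LABA use will be excluded".

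The strength and device appear in criterion 2, which governs cohort entry: patients must be "concurrently on ICS+Tiotropium (specifically Tiotropium Respimat® 1.25 mcg) or ICS/LABA". Tio is not in the abbreviation list and has no formal definition. Section 7 uses the molecule name for two devices ("In investigating Tiotropium (Handihaler and Respimat) for the treatment of asthma"), whereas section 9.5 counts the Tio group by claims for the 1.25 mcg product.

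ICS/LABA is not defined as a fixed-dose product. Sections 8 and 9.3.1 describe the comparator as LABA taken together with ICS. Section 9.5 and the abstract add that the Tio group will be limited to patients on concurrent ICS monotherapy, but this is not among the criteria in section 9.1.

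For adjustment, Table 1 defines other asthma medications as "Leukotriene modifiers" only. It also has an inhaled-medication row that names no class and that the matching lists in section 9.3.3 and the abstract omit.

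**The concern.** A new-user design should compare patients at the start of the treatments under study, with follow-up covering the early period in both arms. Someone already taking a drug of the same class has tolerated it and stayed on it, so the early event risk may differ from that of a true starter.

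A baseline user of another LAMA raises two problems. If that patient changes to Tio, a prevalent class user is counted as a new user. If that patient starts ICS/LABA and continues the LAMA, the LABA arm carries LAMA exposure. The exposure windows in section 9.1 are defined for the study drugs, so they would not register a continuing non-study LAMA. Either case moves the comparison away from starting Tio versus starting LABA, each on top of ICS. Nothing in the plan suggests that the two arms would be affected equally.

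**Working it through.** **Step 1. Who passes criterion 7?** The text was checked for each type of baseline user.

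| Baseline use | Excluded by criterion 7? | Why |
|---|---|---|
| Another LAMA | No, on any reading | Neither Tio nor ICS/LABA covers it, and no other criterion names it |
| Another tiotropium strength or device | Ambiguous | Criterion 2 ties 1.25 mcg to entry; criterion 7 gives no strength; section 7 uses the name for both devices; section 9.5 counts only 1.25 mcg |
| ICS plus a separate LABA, then a fixed ICS/LABA product | Ambiguous | Under the wording of sections 8 and 9.3.1 this may already be prior ICS/LABA use |
| ICS plus a separate LABA, then Tio added | Ambiguous | As above; the ICS-monotherapy restriction in section 9.5 may also remove it, or may describe only the ICS product |

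**Step 2. Do other rules close the gap?** Criterion 3 reads: "Patients with least two diagnosis of COPD at any time during the study period will be excluded". Section 9.5 gives counts before and after the COPD exclusion:

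- Tio: 25,291 − 17,882 = 7,409 removed; 7,409 / 25,291 = 29.3%.
- ICS/LABA: 1,125,657 − 921,804 = 203,853 removed; 203,853 / 1,125,657 = 18.1%.

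This exclusion is large and plausibly takes out some users of other LAMAs. Criterion 3 still leaves patients with one COPD diagnosis or none, whatever their LAMA history.

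**Step 3. Does matching close it?** The covariates nearest to the problem are inhaled medication use (Table 1 only, no class named), other asthma medications (leukotriene modifiers), the number of unique medications, rescue medication use and days on ICS monotherapy. Each may correlate with prior LAMA or LABA use, but none identifies it. A standardized mean difference below 0.1 on these items would not show balance on prior class use.

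**Step 4. Size.** The documents give no counts of such patients, so both inputs are assumptions: q, their share of one arm, and h, their hazard relative to true new users. As a simple mixture, that arm's hazard is multiplied by 1 + q(h − 1).

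| q | h = 0.7 | h = 1.5 |
|---|---|---|
| 5% | 1 + 0.05 × (−0.3) = 0.985 | 1 + 0.05 × 0.5 = 1.025 |
| 15% | 1 + 0.15 × (−0.3) = 0.955 | 1 + 0.15 × 0.5 = 1.075 |

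With the other arm unaffected, the hazard ratio shifts by the same factor or its inverse, depending on which arm is affected. With the same q and h in both arms, the factors cancel.

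**The case against.** Four arguments can be made for the plan.

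First, criterion 7 washes out both study regimens, which is a legitimate meaning of new user; a class-level washout is a design preference. That is fair, and it is why this point is an improvement rather than an error. But criterion 7 already excludes prior users of either regimen from both arms, so it aims for patients new to both add-on options, and another LAMA falls outside that aim.

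Second, a reader might infer that Tio in criterion 7 means only the 1.25 mcg Respimat product, so that users of other strengths or devices certainly enter. The documents do not support that. The restriction belongs to the entry criterion, and prior Tio can equally be read as any tiotropium.

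Third, a reader might infer that users of a separate LABA inhaler certainly enter, putting three-drug patients in the Tio arm. That is not established either. The comparator wording may already count ICS plus separate LABA as ICS/LABA, and the ICS-monotherapy restriction may remove such Tio starters. What stands is that the rule is undetermined, and that the restriction is missing from the eligibility list.

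Fourth, the COPD exclusion and the generic covariates reduce the problem, the magnitude is assumed, and shifts in the same direction in both arms partly cancel. All of this stands. It limits the size of the problem but does not close the gap.

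**Conclusion.** Followed as written, the washout admits baseline users of another LAMA to either arm of a study labelled new-user, and no matching covariate names prior LAMA or LABA use. That holds on every reading. For other tiotropium strengths or devices, and for ICS plus a separate LABA inhaler, the finding is ambiguity in an eligibility rule, not proof that such patients enter.

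The likely effect is small to moderate: one arm's hazard shifts by a factor of 0.985 to 1.025 at a 5% share and 0.955 to 1.075 at 15%. This rests on assumed shares and relative hazards, with one arm affected and the other not. The true number of affected patients cannot be derived from the documents. The change is worth making because it is cheap and should be settled before the cohorts are built and matched.

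**What to change.** 1. Reword criterion 7 to exclude any patient with a claim in the 6-month baseline for a LAMA- or LABA-containing product: any tiotropium strength or device, any other LAMA, and LABA alone or in any combination. List the products in an appendix so that the rule can be coded in only one way.
2. Carry the ICS-monotherapy restriction from section 9.5 into the section 9.1 criteria, and say whether it bars a separate LABA.
3. Require no claim for the other class on the index date in either arm.
4. Report the number excluded by product class in the attrition table that section 9.7.1 already plans.

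The programming cost is a longer drug-code list in an existing step. The sample cost falls on both arms and cannot be quantified from the documents. It is not confined to prevalent users: a prior LABA user starting Tio, or a prior LAMA user starting ICS/LABA, is a true starter of the index drug and would also be lost. The results would then apply to patients new to both classes.

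### No explicit asthma-severity measure is in the propensity score or the balance table; severity is covered only by proxies, so residual confounding of the hazard ratio is possible and would go unseen

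*Combined protocol and SAP*

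**What the plan says.** The background (section 7) states: "Stepwise treatment approach depending on control and severity levels has been the corner stone of asthma therapy". Both control and severity are named.

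Section 9.1 gives the baseline measures as demographics, comorbidity, "inhaled medication use, and control level as defined in Table 1", and then adds ICS dose level. Section 9.3.3 opens its list with "The covariates included in the PSM will be", and the abstract carries a near-identical list. None of these places has an item named or defined as asthma severity.

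The related items that are matched on are:
- Control status (Table 1). A patient is not well controlled "if patient has any one of the following events": an OCS prescription, an asthma-related ER visit or an asthma-related hospitalization. Otherwise the patient is well controlled.
- ICS dose level (Table 1): "Daily dose of ICS classified as low dose ICS, medium dose ICS, and high dose ICS".
- ICS history as yes/no, and its duration: "Days on ICS monotherapy prior to index date".
- Inhaled medication use (Table 1), rescue medication use (9.3.3 and abstract), leukotriene modifiers, and all-cause resource use.

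Patients on biologics in the 6 months before index are excluded. Eligibility criterion 1 reads: "Patients with least two asthma diagnosis (ICD 9 CM: 493.xx or ICD 10: J45-J45.999) will be included". The plan describes no other use of those codes.

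**The concern.** If severity influences which of the two regimens a patient receives and also raises the risk of an asthma hospitalization or ER visit, it is a confounder. Any part of it that the matched variables do not capture stays in the primary hazard ratio, in the moderate-or-severe hazard ratio and in the HCRU comparison.

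The plan has no step that would reveal this. The significance tests and the SMD < 0.1 rule apply to the recorded baseline measures. The remedies at the end of section 9.1 (adding covariates to the Cox model, matching on interaction terms, or discontinuing) start only when a difference is found after matching. A variable that is not listed cannot trigger them. The Cox model otherwise adds only time-varying exposure. Section 9.9 mentions missing clinical detail in general terms but names neither severity nor confounding by indication.

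**Working it through.** The plan gives no power, event-rate or bias figure to reproduce, so the check is mainly a comparison of passages.

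**1. What the proxies can and cannot separate.**
- *Control status* is binary. One OCS prescription counts the same as several asthma hospitalizations, and no asthma-specific event count is matched on.
- *ICS dose level* has no stated time window. ICS history is coded yes/no, so patients without prior ICS monotherapy are allowed for, and criterion 7 removes anyone with ICS/LABA in the 6-month baseline. For a patient with no baseline ICS, the dose can come only from the treatment started at index. It is then part of the exposure rather than a pre-treatment marker.
- *All-cause resource use* is described in 9.3.3 as presence or absence of hospitalizations, ER visits or outpatient visits. Read as one composite, it separates few patients in a cohort that needs two asthma diagnoses.
- *Leukotriene use* is binary, and the *biologic exclusion* removes only part of the severe end.

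Severity is therefore partly adjusted for, but not measured.

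**2. Illustration of size. All inputs are assumptions; the documents give no severity mix and no severity-exacerbation association.** For one binary severity marker with prevalence p1 and p0 in the matched arms and risk ratio RR:

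bias factor = [1 + p1(RR − 1)] / [1 + p0(RR − 1)]

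SMD = (p1 − p0) / √{[p1(1 − p1) + p0(1 − p0)] / 2}

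Take p0 = 0.30 and p1 = 0.35:
- SMD = 0.05 / √[(0.2275 + 0.2100)/2] = 0.107
- RR 1.5: 1.175/1.150 = 1.022
- RR 2.0: 1.350/1.300 = 1.038
- RR 2.5: 1.525/1.450 = 1.052

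A second set with p0 = 0.20 and p1 = 0.25 (SMD 0.120) gives 1.023 at RR 1.5, 1.042 at RR 2 and 1.071 at RR 3.

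**3. What the plan's own SMD limit would still allow.** With p0 = 0.30, an SMD of exactly 0.1 corresponds to p1 of about 0.347, and the factor is 1.020 at RR 1.5 and 1.048 at RR 2.5. Listing severity would therefore not remove a small imbalance. Its value is that a larger one would be seen and would trigger the remedies.

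**4. Room to match.** After the COPD exclusion, section 9.5 gives 17,882 tiotropium and 921,804 ICS/LABA patients, a ratio of 921,804/17,882 = 51.5. Full 1:2 matching would use at most 2 × 17,882 = 35,764 comparators, or 35,764/921,804 = 3.9% of the pool. Both counts precede the remaining exclusions.

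**The case against.** The strongest reply has four parts.

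*The sentence in section 7 is about choosing a treatment step, not about LAMA versus LABA within a step.* The guideline text in section 7 places ICS+LAMA as an alternative in Steps 3 and 4, alongside ICS-LABA regimens. This stands as far as it goes and narrows the expected contrast. But the step table, although its text is broken, also shows ICS-LABA at higher steps, so the two regimens need not cover the same range of disease.

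*The proxies already carry much of severity.* This also stands. ICS dose and controller use largely separate the guideline steps. A reader might infer that severity is not adjusted for at all; the documents do not support that. The proxies are incomplete, for the reasons shown above.

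*The sizes are assumed.* This stands. With the same formula, gaps of 40% or 50% against 30% give SMDs of 0.21 and 0.42 and shifts of 4-10% and 9-21% for RR 1.5-2.5. A reader might take these as the expected bias. Nothing in the documents supports gaps that wide after matching on the proxies, or says which arm would be the more severe.

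*The J45 grading is not in the documents.* This stands. A reader might infer that a severity grade is already in the extracted data. The plan gives only a code range and also accepts ICD-9 493.xx, so the grading is an assumption to be checked. The gap itself does not depend on it, because asthma event counts and pre-index ICS dose can be built from claims the plan already uses.

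**Conclusion.** The concern holds in a limited form. The protocol names severity as a basis for treatment choice, yet no explicit severity measure enters the matching or the balance table. Residual confounding of the hazard ratio by severity is possible, and its balance is never checked.

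Direction and size cannot be determined from the documents. The figure of about 2-5% at a residual SMD near 0.1 is an illustration. It assumes one binary marker, a prevalence near 30%, a risk ratio of 1.5-2.5 conditional on the matched covariates, and a risk-ratio formula that approximates the hazard ratio when events are uncommon. Good proxies would shrink it. The documents do not show that the planned comparison is biased. This is an inexpensive improvement that should be made before matching.

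**What to change.** Add a baseline severity measure to Table 1, section 9.3.3 and the abstract list, adjusted by PSM and held to the existing SMD < 0.1 rule before and after matching:

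(a) Match on baseline counts of asthma-related hospitalizations, asthma-related ER visits and OCS prescriptions, rather than only the yes/no control flag. Define ICS dose level from pre-index claims, with a 'no prior ICS' category. This part needs no diagnosis sub-codes.

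(b) If the programmer confirms that J45 sub-codes grade severity, add the highest sub-code recorded in the baseline period, with a single category for 'unspecified / ICD-9 only / no baseline asthma code'. The last element is needed because criterion 1 sets no time window for the two diagnoses. One pooled category is preferable because the ICS/LABA window opens in July 2014 and the tiotropium window in October 2015. A separate ICD-9 level could act as a calendar marker for one arm and overlap with index year, which is already matched on.

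(c) Report a sensitivity analysis in patients with a specified grade, re-matched within that subgroup so that the 1:2 sets are not broken.

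Section 9.9 should also name severity as a possible residual confounder and label any bias percentage as assumption-based.

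Cost: a few more variables from claims already extracted, and possibly a few lost matches, which should be minor given the comparator pool. Sub-codes may be largely unspecified, or absent for early index dates, so (b) may be only partly informative. The subgroup in (c) is a selected one.
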